10.3.3. Reporting Process & Standards

Reporting Process					
Software					
The currently sup	oported versions of SAS software SAS 9.4 will be used.				
Reporting Area					
HARP Server	: uk1salx00175				
HARP Area	: gsk3128349/res117169/final				
QC Spreadsheet	: gsk3128349/res117169/final/qc				
Analysis Datasets					
Analysis datasets will be created according to Legacy GSK A&R dataset standards					
Generation of RTF Files					
RTF files will be g	generated for all the tables				

Reporting Standards

General

- The current GSK Integrated Data Standards Library (IDSL) will be applied for reporting, unless otherwise stated:
 - 4.03 to 4.23: General Principles
 - 5.01 to 5.08: Principles Related to Data Listings
 - o 6.01 to 6.11: Principles Related to Summary Tables
 - 7.01 to 7.13: Principles Related to Graphics

Formats

- All data will be reported according to the actual treatment the subject received unless otherwise stated.
- GSK IDSL Statistical Principles (5.03 & 6.06.3) for decimal places (DP's) will be adopted for reporting of data based on the raw data collected.
- Numeric data will be reported at the precision collected on the eCRF.
- The reported precision from non eCRF sources will follow the IDSL statistical principles.

Planned and Actual Time

- Reporting for tables, figures and formal statistical analyses :
 - Planned time relative to dosing will be used in figures, summaries, statistical analyses and calculation of any derived parameters, unless otherwise stated.
 - The impact of any major deviation from the planned assessment times and/or scheduled visit days on the analyses and interpretation of the results will be assessed as appropriate.
- Reporting for Data Listings:
 - Planned and actual time relative to study drug dosing will be shown in listings (Refer to IDSL Statistical Principle 5.05.1).
 - Unscheduled or unplanned readings will be presented within the subject's listings.
 - Visits outside the protocol defined time-windows (i.e. recorded as protocol deviations) will be included in listings but omitted from figures, summaries and statistical analyses.

Reporting Standard	S					
Unscheduled Visits						
Unscheduled visi	ts will not be included in summary tables.					
Unscheduled visi	ts will not be included in figures.					
All unscheduled v	visits will be included in listings.					
Descriptive Summa	ry Statistics					
Continuous Data	Refer to IDSL Statistical Principle 6.06.1					
Categorical Data	N, n, frequency, %					
Reporting of Pharm	acokinetic Concentration Data					
Descriptive	Refer to IDSL Statistical Principle 6.06.1					
Summary Statistics	Assign zero to NQ values (Refer to GUI_51487 for further details)					
Reporting of Pharm	acokinetic Parameters					
Descriptive Summary Statistics (Log Transformed)	 N, n, geometric mean, 95% Cl of geometric mean, standard deviation (SD) of logged data and [between and or within] geometric coefficient of variation (CVb/w (%)) will be reported. [1] CV_b (%) = √ (exp(SD²) - 1) * 100 (SD = SD of log transformed data) 					
Parameters Not	Tmax					
Being Log						
Transformed						
Graphical Displays						
Refer to IDSL Sta	atistical Principals 7.01 to 7.13.					

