4.1.1. PET/CT Image Acquisition Workflow

4.1.2. PET scans

- Details of the procedures for the acquisition of PET scans and co-localisation low dose CT scans will be included in the Image Acquisition Guidelines. Each PET scan will have a typical duration of up to 60 minutes.
- PET scan data from the first two subjects will be analysed and used for a potential refinement of the radiation dose estimates and post dose scan time points for subsequent subjects.
- Radioactivity measurements from blood will also be used for dosimetry calculations in first 2 subjects (see Section 7.1 Time & Events Table).

Subject	Scan Times
1 st Subject	Following completion of the IV infusion the subject will be scanned at the following times:
	$1 \text{ hr} \pm 30 \text{ min}$
	$6 \text{ hrs} \pm 1 \text{ hr}$
	$24 \text{ hrs} \pm 1 \text{ hr} (\text{Day } 2)$
	5 days (Day 6)
2 nd Subject	Following completion of the IV infusion the subject will be scanned at the following times:
	$3 hrs \pm 30 min8 hrs \pm 1 hr$
	3 days (Day 4)
	5 days (Day 6)
Remaining Subjects	Four to six additional subjects will undergo scanning, utilising modified scan timings such that the biodistribution is fully profiled over the time period of up to 10-12 days post dosing. A maximum of 4 PET/CT scans will be undergone by each subject.

Table 1PET scanning times

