6. STUDY TREATMENT

The term 'study treatment' or ⁽⁸⁹Zr-GSK3128349' is used throughout the protocol to describe the drug product, which is a mix of ⁸⁹Zr labeled and unlabelled GSK3128349 received by the subjects as per the protocol design. Details of ⁸⁹Zr labelled GSK3128349 can be found in the relevant non Investigational Medicinal Product (IMP) document.

Product name:	⁸⁹ Zr-GSK3128349						
Formulation	50 mM sodium acetate buffer and 200 mM sucrose at pH						
Description:	5.20-5.80, associated with about 15 MBq of radioactivity.						
Dosage Form:	Solution for IV administration						
Unit Dose	Approximately 10 mL of 0.1mg/mL ⁸⁹ Zr-GSK312834						
Strength							
Dose level	1 mg						
Route/	IV as a continuous infusion over 20 mins						
Administration/							
Duration:							
Dosing	Single dose						
Instructions:							
Physical	Liquid in 50mL vial						
Description:							
Manufacturer/	VUMC, Amsterdam						
Source of							
procurement:							

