a. Each PET/CT scan must be preceded by heart rate and blood pressure assessments. b. For subsequent subjects (3rd and beyond) timings of PET scans will be based on data analysis from subjects 1 and 2 and may be carried out anytime between 1 and 10-12 days post injection. A maximum of 4 PET scans will be conducted in each subject. c. Pre-dose urine will not be retained. d. 24 hour urine collection. Total volume will be measured. Part of urine sample will be used for scintillation counting. An aliquot will be utilized for UPCR assessment and another stored for later MS PK analysis if required. Based on data from first 2 subjects, urine may be collected for longer than 24 hrs post dose for subsequent subjects. e. Aliquot from 24 hr collection sample, taken after 24 hr collection is complete. f. Triplicate measurement g. Prior to discharge h. Aliquot from MS PK blood sample							12 days iother						

i. Urine sample to be collected prior to discharge

Note: all time points are relative to start of infusion administration.

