10.8.6. PET Figures

Efficacy	/: Figures				
No.	Population	IDSL / TST ID / Example Shell	Title	Programming Notes	Deliverable [Priority]
2.1.	РК	FIG1	Individual Subject Single Panel Plot : Mean SUV over Time	Y-axis: Result X-axis : Planned Time Points	SAC
2.2.	PK	FIG1	Individual Subject Single Panel Plot : Peak SUV over Time	Y-axis: Result X-axis : Planned Time Points	SAC
2.3.	PK	FIG1	Individual Subject Single Panel Plot : Max SUV over Time	Y-axis: Result X-axis : Planned Time Points	SAC
2.4.	PK	FIG2	Mean Profile (mean +/- SE) Plot : Mean SUV over Time	Y-Axis :Mean +/- SE X- Axis: Time Points	SAC
2.5.	PK	FIG2	Mean Profile (mean +/- SE) Plot : Peak SUV over Time	Y-Axis :Mean +/- SE X- Axis: Time Points	SAC
2.6.	PK	FIG2	Mean Profile (mean +/- SE) Plot : Max SUV over Time	Y-Axis :Mean +/- SE X- Axis: Time Points	SAC
2.7.	PK	FIG1	Percent Injected Dose over time	Y-Axis : Percent Injected Dose X-axis : Time Points	SAC

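### PET time-course figures and any PET model default to planned scan time, although scan start may differ from plan by up to 50% at 1 h (subject 1 only) and 12.5% to 17% at 3 to 8 h, and actual times are already listed.

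*SAP*

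**What the plan says.** SAP 10.3.3 gives the general rule: "Planned time relative to dosing will be used in figures, summaries, statistical analyses and calculation of any derived parameters, unless otherwise stated". SAP 8.1.3.1 makes an exception for non-compartmental PK parameters, which use actual sampling times. The PET sections (SAP 7.1.1 to 7.1.2.2) make none. In SAP 10.8.6 the programming note for the individual-subject Figures 2.1 to 2.3 reads "X-axis : Planned Time Points". Figures 2.4 to 2.7 refer only to time points, so the default applies to them.

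Protocol 4.1.2, Table 1, fixes the schedule for two subjects. Subject 1 is scanned at 1 h ± 30 min, 6 h ± 1 h, 24 h ± 1 h and 5 days. Subject 2 is scanned at 3 h ± 30 min, 8 h ± 1 h, 3 days and 5 days. The day-3 and day-5 scans carry no window. On duration the same section says: "Each PET scan will have a typical duration of up to 60 minutes". For the third subject onward, the SAP 10.2.1 footnote says scans "may be carried out anytime between 1 and 10-12 days post injection", with timings to be chosen after the first two subjects and no windows given.

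The time origin differs between places. Table 1 is introduced with "Following completion of the IV infusion the subject will be scanned at the following times", whereas SAP 10.2.1 carries the line "Note: all time points are relative to start of infusion administration". Protocol Section 6 describes dosing as "IV as a continuous infusion over 20 mins".

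SAP 10.3.3 also puts both planned and actual times in the listings, leaves visits outside protocol windows out of figures and analyses, and promises a review of major timing deviations where appropriate.

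**The concern.** The primary objective is biodistribution over time, so the time axis is part of the primary result. A nominal label helps when subjects are pooled at a common time point. It does nothing for an individual-subject curve, where nothing is pooled and the true time is known. With six to eight subjects and at most four scans each, a displaced early point does not average out within a curve.

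The SAP already accepts the principle elsewhere. Protocol 9.4.2 had PK parameters calculated from nominal times, and SAP 8.1.3.1 uses actual times. The primary PET endpoint is left on the less accurate basis.

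The existing safeguards do not cover this. A scan at 0.5 h under a 1 h label is within its window, so it is neither omitted nor counted as a deviation. For later subjects no window is stated, so the omission rule cannot be applied from these documents.

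At stake are the shape of the early part of the individual uptake curves and the time covariate of any mixed-effects model, which the SAP synopsis keeps in case the data permit.

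**Working it through.** The plan states no timing-error figure, so there is nothing to reproduce. The check is direct arithmetic on the protocol's own windows.

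**Inputs.** Planned time *p* and half-window *w* (Protocol Table 1); scan duration up to 1 h (Protocol 4.1.2); infusion 20 min = 0.33 h (Protocol Section 6); ⁸⁹Zr half-life 3.3 days = 79.2 h (Protocol 4.1).

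**Assumptions.** The Table 1 windows refer to scan start, which the table does not say. The last two columns take a scan of the full 60 minutes, which is an upper bound.

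**Formulas.**
- Start-time error = *w* / *p*
- Largest mid-scan error = (*w* + 0.5) / *p*
- Largest mid-scan error if the scan is timed from the end of infusion but the label is read from its start = (*w* + 0.5 + 0.33) / *p*

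| Scan | *w* (h) | Start | Mid-scan | Mid-scan plus origin shift |
|---|---|---|---|---|
| 1 h, subject 1 | 0.5 | 0.5/1 = 50% | 1.0/1 = 100% | 1.33/1 = 133% |
| 3 h, subject 2 | 0.5 | 0.5/3 = 17% | 1.0/3 = 33% | 1.33/3 = 44% |
| 6 h, subject 1 | 1 | 1/6 = 17% | 1.5/6 = 25% | 1.83/6 = 31% |
| 8 h, subject 2 | 1 | 1/8 = 12.5% | 1.5/8 = 19% | 1.83/8 = 23% |
| 24 h, subject 1 | 1 | 1/24 = 4% | 1.5/24 = 6% | 1.83/24 = 8% |

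The start column needs only the window. The other two are limits, reached when every offset falls in the same direction.

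**Reach of the 50% figure.** It applies to one scan out of at most 6 × 4 = 24 to 8 × 4 = 32, unless later subjects are also scanned at 1 h.

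**Which quantities use time.** By SAP Table 4, SUV is tissue concentration at the scan's own time divided by injected dose per kilogram. Activity and percent injected dose are likewise values at that time. Planned time enters none of these definitions. Organ and effective dose do need an integral over time; the SAP does not say which times feed it. The mean life of ⁸⁹Zr is 79.2 / ln 2 = 114.3 h. A shift of 0.5 h is 0.5/114.3 = 0.4% of that, and the largest shift above, 1.33 h for the 1 h scan, is 1.33/114.3 = 1.2%. If most of the integral is governed by physical decay, the effect on dose is therefore about 1% or less.

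**The case against.** The strongest reply is that this affects display and not data. The measured values are correct, the actual times are in the listings (the PET2 shell has a column for them), and SAP Table 3 schedules no PET statistical analysis. The large percentage belongs to one scan in one subject, and from 24 h onward the start error is at most 4% where a window is given. All of that stands. It limits the size of the point but gives no reason to keep planned time on an individual-subject axis.

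A reader might infer three stronger things that the documents do not support.

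- *That early uptake is itself wrong by nearly half.* This comes from putting the albumin exchange rate in Protocol 2.1 (4% to 5% of total albumin per hour, extravascular pool about twice the intravascular) into a two-pool model. The model's extravascular share does move steeply around 1 h, but no SAP endpoint is an extravascular share. The intravascular share under the same model moves only about 2% to 7% across the 1 h window, depending on how the rate is read. The protocol itself calls the pool description a simplification.
- *That PET derived values are miscalculated.* The uptake parameters do not use planned time, as shown above.
- *That the PBPK model is harmed.* SAP Appendix 8 contains no PBPK output, and modellers can take actual times from the listings.

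One might also argue that different body regions are imaged at different moments within a scan and need separate timestamps. Acquisition order and transferred time fields belong to the Image Acquisition Guidelines and the vendor agreement, which are not among these documents, so the point cannot be sized here.

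**Conclusion.** The point holds as a modest but specific reporting correction. PET figures, and PET models if they are run, would use planned time by default, while PK parameters use actual time. The permitted start-time error is 50% at 1 h for subject 1, 17% at 3 h and 6 h, 12.5% at 8 h and 4% at 24 h. It is unbounded by the plan for the day-3 and day-5 scans and for subjects three onward. Scan duration and the unresolved origin can add to these figures, under the assumptions stated with the table.

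The error lies in the time coordinate only. SUV, activity and percent injected dose are unaffected. The dose effect of about 1% assumes that physical decay dominates the time integral, and that planned times were used at all, which the SAP does not say.

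The mismatch between end and start of infusion is a separate inconsistency of 20 minutes, one third of the 1 h label. It must be reconciled whichever time basis is used.

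**What to change.** 1. **Reconcile the origin.** Protocol Table 1 and the Time and Events note should count from the same event, and the SAP should name it.
2. **SAP 10.3.3.** Add an exception: individual PET Figures 2.1 to 2.3 and 2.7, and mixed-effects models of PET parameters if fitted, use actual elapsed time from the defined origin, taken at mid-acquisition where available and otherwise at scan start.
3. **SAP 10.8.6.** Change the x-axis programming notes for Figures 2.1 to 2.3 and 2.7 to match.
4. **Leave the rest.** Planned time stays as the row label in the PET summary tables and the axis of the mean plots (Figures 2.4 to 2.6), where a common label is needed for pooling.

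The cost is one SAP sentence, four programming notes and one reconciled definition. Actual times are already due to be listed. Using mid-acquisition also requires confirming that the vendor file carries scan start and end times; if it does not, scan start still removes the window error. No new subject procedures are needed.

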10.4. Appendix 4: Derived and Transformed Data

10.4.1. General

Multiple Measurements at One Time Point

- Mean of the measurements will be calculated and used in any derivation of summary statistics but if listed, all data will be presented.
- If there are two values within a time window the value closest to the target day for that window will be used. If values are the same distance from the target then the mean will be taken.
- Subjects having both High and Low values for Normal Ranges at any post-baseline visits for safety parameters will be counted in both the High and Low categories of "Any visit post-baseline" row of related summary tables. This will also be applicable to relevant Potential Clinical Importance summary tables.

Study Day

- Calculated as the number of days from randomisation date :
 - Ref Date = Missing \rightarrow Study Day = Missing
 - Ref Date < Randomisation Date \rightarrow Study Day = Ref Date Randomisation Date
 - Ref Data ≥ Randomisation Date → Study Day = Ref Date (Randomisation Date) + 1

10.4.2. Study Population

Demographics

Age

- Screening date will be used as a reference date for calculating age.
- GSK standard IDSL algorithms will be used for calculating age where birth date will be imputed as follows:
 - o Any subject with a missing day will have this imputed as day '15'.
 - Any subject with a missing date and month will have this imputed as '30th June'.
- Birth date will be presented in listings as 'YYYY'.

Body Mass Index (BMI)

• Calculated as Weight (kg) / [Height (m)]²

10.4.3. Safety

ECG Parameters				
RR Interval				
 IF RR interval (msec) is not provided directly, then RR can be derived as : [1] If QTcB is machine read & QTcF is not provided, then : 				
$RR = \left[\left(\frac{QT}{QTcB} \right)^2 \right] * 1000$				
[2] If QTcF is machine read and QTcB is not provided, then:				

ECG Parameters
$RR = \left[\left(\frac{QT}{QTcF} \right)^3 \right] * 1000$
• If ECGs are manually read, the RR value preceding the measurement QT interval should be a collected value THEN do not derive.
Corrected QT Intervals
• When not entered directly in the eCRF, corrected QT intervals by Bazett's (QTcB) and Fredericia's (QTcF) formulas will be calculated, in msec, depending on the availability of other measurements.
• IF RR interval (msec) is provided then missing QTcB and/or QTcF will be derived as :
$QTcB = \frac{QT}{\sqrt{\frac{RR}{1000}}} \qquad \qquad QTcF = \frac{QT}{3\sqrt{\frac{RR}{1000}}}$

10.5. Appendix 5: Premature Withdrawals & Handling of Missing Data

10.5.1. Premature Withdrawals

Element	Reporting Detail
General	 Subject study completion (i.e. as specified in the protocol) was defined as one who has completed all phases of the study including the follow-up visit. The end of the study is defined as the last subject's last visit. Withdrawn subjects may be replaced in the study. All available data from subjects who were withdrawn from the study will be listed and all available planned data will be included in summary tables and figures, unless otherwise specified.

10.5.2. Handling of Missing Data

Element	Reporting Detail
General	 Missing data occurs when any requested data is not provided, leading to blank fields on the collection instrument : These data will be indicated by the use of a "blank" in subject listing displays. Unless all data for a specific visit are missing in which case the data is excluded from the table. Answers such as "Not applicable" and "Not evaluable" are not considered to
	be missing data and should be displayed as such.
Outliers	• Any subjects excluded from the summaries and/or statistical analyses will be documented along with the reason for exclusion in the clinical study report.

10.5.2.1. Handling of Missing Dates

Element	Reporting Detail
General	Partial dates will be displayed as captured in subject listing displays.
Adverse Events	 The eCRF allows for the possibility of partial dates (i.e., only month and year) to be recorded for AE start and end dates; that is, the day of the month may be missing. In such a case, the following conventions will be applied for calculating the time to onset and the duration of the event: Missing Start Day: First of the month will be used unless this is before the start date of study treatment; in this case the study treatment start date will be used and hence the event is considered On-treatment as per Appendix 4: Treatment States and Phases. Missing Stop Day: Last day of the month will be used, unless this is after the stop date of study treatment; in this case the study treatment stop date will be used. Completely missing start or end dates will remain missing, with no imputation applied. Consequently, time to onset and duration of such events will be missing.

Element	Reporting Detail
	• Start or end dates which are completely missing (i.e. no year specified) will remain missing, with no imputation applied.

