10.5.2.2. Handling of Partial Dates

Element	Reporting Detail
Concomitant Medications	 Partial dates for any concomitant medications recorded in the CRF will be imputed using the following convention: If the partial date is a start date, a '01' will be used for the day and 'Jan' will be used for the month If the partial date is a stop date, a '28/29/30/31' will be used for the day (dependent on the month and year) and 'Dec' will be used for the month. The recorded partial date will be displayed in listings.
Adverse Events	 Any partial dates for adverse events will be raised to data management. If the full date cannot be ascertained, the following assumptions will be made: If the partial date is a start date, a '01' will be used for the day and 'Jan' will be used for the month. However, if these results in a date prior to Week 1 Day 1 and the event could possibly have occurred during treatment from the partial information, then the Week 1 Day 1 date will be assumed to be the start date. The AE will then be considered to start on-treatment (worst case). If the partial date is a stop date, a '28/29/30/31' will be used for the day (dependent on the month and year) and 'Dec' will be used for the month.

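### SAP 10.5.2.1 sets a missing AE stop day to Day 1, before onset for any later-starting AE; 10.5.2.2 adds an unranked second rule, and Study Day counts from randomisation instead of dosing

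*SAP*

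**What the plan says.** SAP 10.5.2.1 (Handling of Missing Dates) states its scope: "The eCRF allows for the possibility of partial dates (i.e., only month and year) to be recorded for AE start and end dates". It also states its purpose: "the following conventions will be applied for calculating the time to onset and the duration of the event". For a missing stop day the rule is: "Last day of the month will be used, unless this is after the stop date of study treatment". When month-end does fall later than that, a cap applies: "in this case the study treatment stop date will be used". A missing start day becomes the first of the month, or the treatment start date if that is later. The event is then on-treatment "as per Appendix 4: Treatment States and Phases". The SAP's Appendix 4 has no such part; it covers General, Study Population and Safety.

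SAP 10.5.2.2 (Handling of Partial Dates) opens its AE row with: "Any partial dates for adverse events will be raised to data management". If the query fails, the last calendar date of the month "will be used for the day (dependent on the month and year", and the same sentence then names December as the month. For a start date it uses day 01 and January, with an exception that begins "However, if these results in a date prior to Week 1 Day 1" and moves the start to that day if the event could have occurred during treatment. This single-dose study has no week-numbered visits.

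SAP 10.4.1 counts Study Day from the randomisation date, adding 1 on or after it. Protocol 6.1 says that there is no randomisation requirement and that randomisation numbers serve internal reporting only. The Time and Events tables (Protocol 7.1.2, SAP 10.2.1) mark Randomisation in the Day -1 column and dosing on Day 1.

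**The concern.** Capping an AE stop date at treatment stop might be tolerable where treatment lasts for weeks. Here treatment lasts 20 minutes, and AEs are collected until the follow-up visit at Day 43 ± 2. The cap therefore pulls the stop date back to dosing for every AE with a missing stop day. The rule exists to calculate duration, and it returns zero or negative durations.

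Two programmers could also follow different sections of the SAP and derive different dates from the same record. A Study Day count that starts before dosing would disagree with the protocol's own day labels.

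**Working it through.** **Inputs.**
- One 20-minute infusion on Day 1 (Protocol 4.1 and 6), so the treatment start and stop dates are both Day 1. The SAP does not define the treatment stop date; this is the natural reading.
- AEs are collected from the start of treatment to follow-up (Protocol 7.3.1.1, 7.1.3).
- Randomisation is scheduled on Day -1, taken as the calendar day before Day 1.
- The documents give no figure of their own to reproduce. The calendar dates below are illustrative.

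**Step 1: the cap in 10.5.2.1.** Take an AE with onset on Day k, where k is at least 1. The end of its stop month is no earlier than its true stop, which is no earlier than Day k. Month-end is therefore either after Day 1, so the cap sets the stop to Day 1, or is itself Day 1. Either way the imputed stop is Day 1.

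Duration = stop - onset + 1 = 1 - k + 1 = 2 - k.

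| Onset day | Imputed duration (days) |
|---|---|
| 1 | 1 |
| 2 | 0 |
| 10 | -8 |
| 31 | -29 |

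**Step 2: the two stop rules on one record.** Dosing is on 11 March, onset on 20 March (Day 10), and the stop is recorded as March. The true duration is between 1 and 12 days.

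| Rule | Imputed stop | Duration (days) |
|---|---|---|
| 10.5.2.1 | 11 March | 11 - 20 + 1 = -8 |
| 10.5.2.2, known month kept | 31 March | 31 - 20 + 1 = 12 |
| 10.5.2.2, December applied literally | 31 December | 286 + 1 = 287 |

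The imputed stop under 10.5.2.2 is 20 days after the capped date on the first reading (31 - 11) and 295 days after it on the second.

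**Step 3: the two start rules.** Dosing is on 11 March and onset is recorded as April. Under 10.5.2.1 the start is 1 April, which is 20 + 1 = 21 days after dosing. Under 10.5.2.2 it is also 1 April if the known month is kept. Read literally it is 1 January, which is before dosing. It then moves to the dosing date, 0 days after dosing, if an April event counts as possibly during treatment.

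**Step 4: Study Day.** With randomisation on 10 March and dosing on 11 March, and reading the formula as a subtraction, dosing falls on Study Day 11 - 10 + 1 = 2. Day -1 becomes Study Day 1. Every post-dose day rises by one:

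| Protocol day | 1 | 2 | 4 | 6 | 13 | 20 | 31 | 43 |
|---|---|---|---|---|---|---|---|---|
| Study Day | 2 | 3 | 5 | 7 | 14 | 21 | 32 | 44 |

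**The case against.** The best defence is that the two sections cover different dates: 10.5.2.1 those lacking only the day, and 10.5.2.2, which fills in both day and month, those lacking both. That reading is possible, so a reader who infers a certain contradiction for the same dates goes too far. Nor can the 12-day result be treated as what 10.5.2.2 says. It rests on taking the reference to month and year to mean that a known month is kept, and the text does not state that.

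Still, 10.5.2.2 is worded for any partial AE date, and 10.5.2.1 itself calls month-and-year dates partial. The overlap is left open. Step 1 does not depend on it.

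The second defence is reach, and it largely stands. Partial dates go to data management first. SAP 10.5.2.1 shows them in listings as captured. No planned AE table summarises duration or time to onset. One might infer that the AE listings will print negative durations, but their shell (CP_AE8) is not reproduced, so the documents do not show that.

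Nor does the Study Day shift disturb PET or PK timing. SAP 10.3.3 uses planned time relative to dosing in summaries and figures, SAP 8.1.3.1 uses actual sampling times for PK parameters, and baselines are defined by visit label. The shift is also conditional: assigning randomisation numbers on the dosing day would remove it.

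**Conclusion.** Minor, but wrong as written. Given that treatment stop is the infusion date, the stop-day rule in SAP 10.5.2.1 places the stop before onset for every AE that starts after Day 1, and gives one day to any AE that starts on Day 1. The relation of 10.5.2.1 to 10.5.2.2 is unclear for both stop and start dates. The size of any conflict depends on the reading, so both results in step 2 should be carried. The Study Day shift is exactly one day, provided that randomisation numbers are assigned on Day -1.

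The effect is confined to derived time to onset and duration for AE dates still partial after query, and to derived Study Day values.

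**What to change.** **AE dates (SAP 10.5.2.1 and 10.5.2.2).** Delete the treatment-stop cap and keep one rule set, applied after query:
- Stop date: last day of the known month; December only if the month is also missing; never before onset.
- Start date: first of the known month; January only if the month is also missing; moved up to the infusion date only when the recorded partial date allows onset on or after dosing. The condition matters because Protocol 7.3.1.1 records some SAEs from consent, before dosing.
- Replace the Week 1 Day 1 label with the infusion date (Day 1).
- Replace the reference to the absent part of Appendix 4 with a statement that onset on or after the start of infusion counts as on-treatment (post-dose).

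**Study Day (SAP 10.4.1).** Anchor it on the infusion date. Days 1 to 43 then keep their protocol numbers.

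The cost is text edits to three SAP sections, the matching date-imputation code and one anchor variable. No new data are needed.
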